Single-center, prospective, dose-escalation clinical trial.

(2) Trial Administration Strategy

A traditional "3+3" dose-escalation design will be adopted. Subjects will be sequentially assigned to one of three dose groups (2×10^{10} units, 1×10^{11} units, 5×10^{11} units per administration, once daily for 4 consecutive days via intranasal instillation). Each dose group initially enrolls 3 subjects, with sequential enrollment (i.e., the next subject is enrolled only after the previous subject completes the 14-day DLT observation period).

- If no DLT is observed in 3 subjects of a dose group, the study proceeds to the next higher dose level.

- If 1 out of 3 subjects experiences DLT, an additional 3 subjects are enrolled in the same dose group. If no DLT is observed in the additional 3 subjects, the study proceeds to the next higher dose level; if ≥ 1 additional subject experiences DLT, the current dose level is defined as the maximum tolerated dose (MTD), and dose escalation is terminated.
- A total of 6 to 18 subjects will be recruited during the dose-escalation phase.

(3) Study Suspension or Early Termination

The study will be suspended or terminated early if any of the following occurs:

- Violation of the *Good Clinical Practice (GCP)* or the *Administrative Measures for Stem Cell Clinical Research (Trial)*;
- Emergence of new safety or efficacy data on MSC-sEVs indicating that the trial poses a serious risk to patient safety or is clearly ineffective;
- Failure to enroll subjects as scheduled for 3 consecutive months;
- Major protocol deviations that affect the validity of study data;
- Request for termination by the sponsor or regulatory authorities.

2. Subject Selection Criteria

(1) Inclusion Criteria

- Confirmed diagnosis of acute ischemic stroke (in accordance with the *Chinese Guidelines for the Diagnosis and Treatment of Acute Ischemic Stroke (2023)*);
- Aged 18-70 years, regardless of gender;
- Anterior circulation occlusion (internal carotid artery, middle cerebral artery M1/M2 segment) confirmed by CTA or MRA;
- mRS score of 0-1 before the current stroke episode (indicating no or minimal disability prior to the index event);
- ASPECTS ≥ 6 on non-contrast computed tomography (NCCT) or diffusion-weighted imaging (DWI) after stroke onset (indicating a small to moderate infarct volume);
- NIHSS score ≥ 6 at screening (indicating moderate to severe neurological deficit);

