1. Neurological Function Scales:

- **NIHSS:** Assesses the severity of neurological deficits (range: 0-42; higher scores indicate more severe deficits). Administered at baseline, Day 7, Day 14, and Day 90.
- **mRS:** Assesses functional independence (range: 0-6; scores 0-2 indicate good functional outcome). Administered at baseline, Day 7, Day 14, and Day 90.
- **Modified Barthel Index (MBI):** Assesses activities of daily living (range: 0-100; higher scores indicate better independence). Administered at baseline, Day 14, and Day 90.
- **EQ-5D-5L:** Assesses health-related quality of life (including mobility, self-care, usual activities, pain/discomfort, anxiety/depression; scored as a utility value ranging from -0.291 to 1.0). Administered at baseline, Day 14, and Day 90.

2. Cerebral Perfusion Parameters (CTP):

- Measured at baseline, Day 14, and Day 90: cerebral blood volume (CBV), cerebral blood flow (CBF), mean transit time (MTT), time to peak (TTP) in the infarct core and penumbra.
- Changes in perfusion parameters from baseline are used to evaluate the improvement of cerebral blood flow.

3. Infarct Volume Measurement:

- Infarct volume is measured on DWI using the ABC/2 method (A: maximum length, B: maximum width perpendicular to A, C: number of slices × slice thickness).
- Changes in infarct volume from baseline to Day 14 are used to evaluate infarct progression or regression.

5. Outcome Evaluation Indicators

(1) Primary Safety Endpoints

- **Dose-Limiting Toxicity (DLT):** Assessed within 14 days of the first dose, defined as any of the following:
 1. Grade 3-4 AE related to the study drug (CTCAE V5.0), such as severe nasal bleeding, anaphylactic reaction, or hepatic injury;
 2. Increase in NIHSS score ≥ 4 points from baseline (indicating significant neurological deterioration);
 3. Symptomatic intracranial hemorrhage (confirmed by CT/MRI and associated with neurological deterioration).

(2) Secondary Safety Endpoints

1. **SAE Incidence:** Proportion of subjects with drug-related SAEs within 90 days of the first dose;
2. **All-Cause Mortality:** Proportion of subjects who die from any cause within 90 days of the first dose;
3. **Laboratory Abnormality Rate:** Proportion of subjects with Grade ≥ 3 laboratory abnormalities (e.g., thrombocytopenia, elevated liver enzymes) within 90 days.

(3) Efficacy Endpoints

1. **Functional Outcome:** Proportion of subjects with mRS score 0-2 at Day 90;

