2. **Neurological Improvement:** Mean change in NIHSS score from baseline to Day 14 and Day 90; proportion of subjects with NIHSS score reduction ≥ 4 points at Day 14;
3. **Functional Independence:** Mean change in MBI score from baseline to Day 90; proportion of subjects with MBI score ≥ 60 (indicating moderate independence) at Day 90;
4. **Quality of Life:** Mean change in EQ-5D-5L utility value from baseline to Day 90.

(4) Exploratory Endpoints

1. **Infarct Volume Change:** Mean change in infarct volume from baseline to Day 14;
2. **Cerebral Perfusion Improvement:** Mean changes in CBF, CBV, MTT, and TTP from baseline to Day 14;
3. **Correlation Analysis:** Correlation between baseline characteristics (e.g., age, NIHSS score) and efficacy outcomes.

6. Study Protocol Flow and Evaluation Indicators

First Visit [Baseline (Day 0)]

1. **Informed Consent:** The investigator explains the study protocol to the subject/legal representative, who signs the informed consent form if willing to participate.
2. **Screening Assessments:**
 - Demographic and clinical data collection;
 - Vital signs measurement;
 - Laboratory tests: CBC, clinical chemistry, coagulation function, serum electrolytes, infectious disease screening, tumor markers, urinalysis, pregnancy test (if applicable);
 - Imaging examinations: NCCT, DWI, MRA/CTA, chest X-ray, 12-lead ECG;
 - Neurological scales: NIHSS, mRS, MBI, EQ-5D-5L.
3. **Eligibility Confirmation:** The investigator reviews the inclusion/exclusion criteria and confirms eligibility.
4. **Study Drug Administration:**
 - Nasal mucosa pretreatment with hyaluronidase (150 U per nostril);
 - Instill the first dose of hUC-MSC-sEV-001;
 - Measure vital signs 30 minutes after administration.
5. **Documentation:** Record combined medications, rehabilitation therapy plans, and any AEs.

Second Visit (Day 7 ± 1)

1. **Safety Assessments:**
 - Vital signs measurement;
 - Laboratory tests: CBC, clinical chemistry, urinalysis;
 - AE monitoring and recording.
2. **Efficacy Assessments:**
 - Neurological scales: NIHSS, mRS.
3. **Documentation:** Record combined medications and rehabilitation therapy progress.

Third Visit (Day 14 ± 2)

1. Safety Assessments:

- Vital signs measurement;
- Laboratory tests: CBC, clinical chemistry, coagulation function, serum electrolytes, infectious disease screening, tumor markers, urinalysis;
- Imaging examinations: 12-lead ECG, DWI, FLAIR, CTA/CTP;
- AE monitoring and recording (including SAE follow-up).

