- **Source Documents:** Medical records, laboratory reports, imaging films, and informed consent forms are stored in the hospital's medical record department or study office for 30 years after study completion.
- **Electronic Data:** The EDC database and backup files are stored on a secure server with restricted access. The data are retained for 30 years after study completion.
- **Statistical Analysis Data:** The locked database and statistical analysis code are stored in a secure location and retained for 30 years after study completion.

11. Statistical Analysis

(1) Statistical Analysis Sets

- **Full Analysis Set (FAS):** Includes all randomized subjects who receive at least one dose of the study drug. Missing efficacy data are imputed using the last observation carried forward (LOCF) method.
- **Per Protocol Set (PPS):** Includes subjects in the FAS who comply with the study protocol (e.g., complete all visits, receive all 4 doses of study drug, no major protocol violations). This set is used for sensitivity analysis of efficacy outcomes.
- **Safety Analysis Set (SAS):** Includes all subjects who receive at least one dose of the study drug. This set is used for safety analyses (adverse events, laboratory abnormalities).

(2) Descriptive Statistics

- **Continuous Variables:** Presented as mean \pm standard deviation (SD) for normally distributed data, or

median (P25, P75) for non-normally distributed data. Examples include age, NIHSS score, and infarct volume.

- **Categorical Variables:** Presented as frequency (percentage). Examples include gender, hypertension status, and mRS score categories (0-2 vs. 3-6).

(3) Inferential Statistics

- **Primary Efficacy Endpoint:** The proportion of subjects with mRS score 0-2 at Day 90 is compared between dose groups using the chi-square test or Fisher's exact test. A generalized linear model is used to adjust for potential confounders (e.g., age, baseline NIHSS score).
- **Secondary Efficacy Endpoints:**
 - Mean changes in NIHSS, MBI, and EQ-5D-5L scores from baseline are compared using repeated measures analysis of variance (ANOVA) or Kruskal-Wallis rank sum test.
 - The proportion of subjects with NIHSS score reduction ≥ 4 points at Day 14 is compared using the chi-square test.
- **Safety Endpoints:**
 - The incidence of AEs and SAEs is compared between dose groups using the chi-square test or Fisher's exact test.

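### The tests named for NIHSS, MBI and EQ-5D-5L change answer different questions, are not tied to the endpoint visits, and leave the collected baseline score and the dose order unused

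*Protocol*

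**What the plan says.** Protocol section 11(3) fixes the method for these three scales in one sentence, which reads as follows: "Mean changes in NIHSS, MBI, and EQ-5D-5L scores from baseline are compared using repeated measures analysis of variance (ANOVA) or Kruskal-Wallis rank sum test". Nothing in it names a visit, a covariate, a dose-trend term or a rule for choosing between the two methods.

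Section 5(3) is specific about timing. The endpoints are "Mean change in NIHSS score from baseline to Day 14 and Day 90", "Mean change in MBI score from baseline to Day 90" and "Mean change in EQ-5D-5L utility value from baseline to Day 90".

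Section 4(3) collects more visits than these. NIHSS is "Administered at baseline, Day 7, Day 14, and Day 90"; MBI and EQ-5D-5L are each "Administered at baseline, Day 14, and Day 90".

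Covariate adjustment appears in section 11(3) only for the mRS 0-2 proportion: "A generalized linear model is used to adjust for potential confounders (e.g., age, baseline NIHSS score").

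On allocation, section 1(2) says "Subjects will be sequentially assigned to one of three dose groups". Each group starts with 3 subjects and is extended by 3 after one DLT. The stated total is 6 to 18.

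**The concern.** There are three separate issues.

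- **Hypothesis and visit.** The dose main effect of a repeated-measures ANOVA averages over the visits included. Kruskal-Wallis takes one value per subject and compares rank distributions. The two can give different answers on the same data, and the sentence does not say which visit or contrast is meant.
- **Baseline.** Without randomisation, and with 3 to 6 subjects per dose, nothing balances the starting score across doses. A change score does not remove the imbalance. A group that starts worse tends to show more change through regression to the mean, and this could be read as a dose effect.
- **Dose order.** Both tests treat three increasing doses as unordered labels, although the study is meant to help choose a dose.

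At stake is how readable the preliminary efficacy signal by dose will be. No decision rule in the protocol depends on these p-values.

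**Working it through.** **Inputs from the protocol.** Three ordered doses with 3 or 6 subjects each; two-sided 0.05 (section 11(5)); visits as in sections 4(3) and 5(3). The protocol gives no SD, effect size or power for these scales, so there is no figure of its own to reproduce.

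**Assumptions.** NIHSS SD 5; correlations baseline-Day 14 0.7, baseline-Day 90 0.5, Day 14-Day 90 0.8; normal scores; a true Day 90 difference of 8 points between low and high dose, linear over the three levels, and half as large at Day 14. All three doses open, so N is 9 or 18.

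**1. Baseline imbalance with 3 per dose.**
SD of the difference between two baseline means = 5 × √(1/3 + 1/3) = 5 × 0.816 = 4.08 points.
Shift in the change difference for an imbalance of that size = (1 − 0.5) × 4.08 = 2.04 points. This arises with no dose effect at all.

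**2. Precision gained by using baseline.**
Variance with baseline as covariate ÷ variance of the change score = (1 − ρ²) / [2(1 − ρ)] = (1 + ρ)/2, that is 0.65, 0.75 and 0.85 at ρ = 0.3, 0.5 and 0.7.
Residual degrees of freedom at N=9: three-group comparison of change 9 − 3 = 6; with baseline added 9 − 4 = 5; linear dose plus baseline 9 − 3 = 6.

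**3. Simulated power, linear 8-point effect, ρ = 0.5.**

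| Test | 3/3/3 | 6/6/6 |
|---|---|---|
| Repeated-measures dose main effect | about 21% | about 50% |
| Three-group ANOVA on Day 90 change | 26% | 60% |
| Same, with baseline as covariate | 28% | 70% |
| Linear trend on change, no baseline | 40% | 74% |
| Linear trend with baseline | 43% | 82% |

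At N=9 nearly all of the gain comes from dose order (26% to 40%); baseline then adds about 3 points. At N=18 baseline adds about 8 points to the trend and 10 to the group comparison. At ρ = 0.7 and N=9, adding baseline to the group comparison lowers power from 40% to 37%.

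**4. Kruskal-Wallis at 3/3/3.** Over all 1,680 arrangements, the chi-square cut-off of 5.991 is reached in 18, so the true size is 18/1,680 = 1.1%. The exact P(H ≥ 5.6) is 84/1,680 = 5.0%. Since the protocol requires P below 0.05, the exact test rejects only from H = 5.689, with size 48/1,680 = 2.9%. With the chi-square approximation, power in the scenario above is about 7%.

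**5. Sensitivity to the assumed scenario.**
If the effect is equal at Day 14 and Day 90, the repeated-measures main effect has 36% against 26% for ANOVA on the Day 90 change at 3/3/3, and 77% against about 60% at 6/6/6. The ranking in step 3 reverses.
If the Day 90 effects are 0/8/4 over the three doses, ANOVA has 26% and the trend with baseline 8% at 3/3/3; at 6/6/6 it is about 60% against 18%.

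**The case against.** The sample size in section 11(4) is built on the 3+3 rule and not on these scales, and the comparisons are secondary. Visit contrasts, covariates and exact versus approximate p-values are often left to the statistical analysis plan, which is not shown. An omnibus test is also defensible where monotone efficacy has not been established. These points stand. They limit the weight of the concern and rule out replacing the group comparison by a single slope, as step 5 shows.

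A reader might infer that the plan contains no test of the Day 90 change. The text does not support that: Kruskal-Wallis applied to the Day 90 change is a permitted reading, and a repeated-measures ANOVA also has visit and dose-by-visit terms. The supportable statement is that the sentence is not tied to the visit. Nor is the repeated-measures option always weaker; it gains power when the effect is constant over visits.

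A reader might also infer that leaving out baseline wastes much of the information. At 9 subjects the power gain is a few points at most and can be negative. The case for baseline there rests on imbalance between sequentially filled groups.

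What the objection does not remove is that the protocol itself fixes two methods with different hypotheses and names adjustment for mRS but not for these scales.

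**Conclusion.** The point holds in a limited form. The protocol names two tests that are not interchangeable, does not link them to the section 5(3) visits, and leaves the collected baseline and the dose order unused. With 3 per dose, a typical chance imbalance of 4.1 NIHSS points moves the change difference by about 2.0 points, assuming SD 5 and correlation 0.5. Baseline adjustment adds about 2 power points to the group comparison at N=9 and 10 at N=18; a trend adds more, but only for a response close to linear.

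All power figures rest on assumed normal NIHSS scores and a large 8-point (1.6 SD) effect. They were not computed for MBI or EQ-5D-5L, which are bounded scales. The protocol's N is 6 to 18; 9 to 18 applies only if all three doses open. No choice of test makes these comparisons confirmatory.

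**What to change.** Reword the secondary-efficacy item in section 11(3):

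- For NIHSS at Day 14 and at Day 90, and for MBI and EQ-5D-5L at Day 90, fit a linear model of the follow-up score on its own baseline score and dose group. Report adjusted estimates by dose with 95% confidence intervals, labelled exploratory.
- Add a linear dose-trend estimate with its confidence interval alongside the group comparison, not in its place.
- Where a rank test is kept, name the visit and use an exact or permutation p-value.

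The cost is wording only, as every score is already collected. The downside is one residual degree of freedom (6 to 5 at N=9), so baseline adds little or nothing there when the correlation is 0.7 or more. The trend estimate is weak if the response is not monotone.

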Statistical Analysis Methods	
The primary objective of this study is to evaluate the safety and preliminary efficacy of hUC-MSC-sEV-001 nasal drops (small extracellular vesicles derived from human umbilical cord mesenchymal stem cells) in the treatment of acute ischemic stroke. Baseline information will be described based on the distribution type of variables: continuous variables will be presented as mean \pm standard deviation, as well as P50, P25, and P75 percentiles; categorical variables will be described using frequency (percentage). For inter-group differences: analysis of variance (ANOVA) or Kruskal-Wallis rank sum test will be used for continuous variables; chi-square test or Fisher's exact test will be used for categorical variables. A generalized linear model will be applied to analyze the difference in the proportion of patients with a modified Rankin Scale (mRS) score of 0-2 at 90 days (± 7 days) between the two groups.

------------------------------	---

Research Background

The prevention and treatment of brain diseases is a major challenge for "Healthy China". While stem cells have made significant progress in the treatment of brain diseases, they have limitations such as immune rejection and poor histocompatibility. Stem cell derivatives, such as exosomes or small extracellular vesicles (sEVs), exhibit similar therapeutic effects to stem cells. Moreover, their low immunogenicity and ability to easily cross the blood-brain barrier give them greater advantages in the treatment of brain diseases.

This research focuses on the therapeutic effects and mechanisms of four types of stem cell-derived sEVs in ischemic stroke and Alzheimer's disease (AD), with the goal of advancing their clinical research and application. The study addresses key scientific issues, including the mechanism by which stem cell-derived sEVs regulate neuronal target cells and immune microenvironment cells *in vivo* to achieve stem cell-like functions. It will also provide a safe and efficient mesenchymal stem cell-derived sEV (MSC-sEV) therapeutic protocol for solving global challenges such as ischemic stroke and AD.

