 - Grade ≥ 3 laboratory abnormalities are summarized as frequency (percentage) by dose group.

(4) Sample Size Justification

This is a phase I dose-escalation study designed to explore the safety and MTD of hUC-MSC-sEV-001. Using the "3+3" design, a sample size of 6-18 subjects is sufficient to identify the MTD with a 90% probability of avoiding overdosing and a 80% probability of identifying the MTD if it exists.

(5) Statistical Software

All statistical analyses are performed using SAS 9.4 software (SAS Institute Inc., Cary, NC, USA). Two-sided tests are used, and a P-value < 0.05 is considered statistically significant.

(6) Interim Analysis

No interim analysis is planned for this study due to the small sample size. The study will be terminated early only if safety concerns arise (e.g., ≥ 2 subjects experience DLT at the same dose level).

12. Quality Control and Assurance

(1) Protocol Compliance

- **Training:** All study personnel (investigator, CRC, monitor, pharmacist) receive training on the study

protocol, GCP, and stem cell clinical research regulations before study initiation. Training records are retained in the study file.

- **Standard Operating Procedures (SOPs):** SOPs are developed for key processes, including subject screening, study drug administration, adverse event reporting, and data management. Study personnel strictly follow the SOPs to ensure consistency.
- **Protocol Deviation Monitoring:** The monitor records all protocol deviations (e.g., missed visits, incorrect dose administration) in the "Protocol Deviation Log". Major deviations are reported to the Ethics Committee and sponsor.

(2) Study Drug Quality Control

- **Manufacturing Quality:** The study drug is produced under GMP conditions, and each batch is tested for purity, potency, sterility, and endotoxin levels. A certificate of analysis (CoA) is provided for each batch.
- **Storage and Transportation:** Temperature monitoring during transportation and storage ensures that the study drug remains within the specified temperature range (-80°C ± 10°C). Temperature records are reviewed and archived.
- **Inventory Management:** The study drug inventory is checked monthly to ensure that the quantity administered matches the quantity received, and to prevent expiration or loss.

(3) Laboratory Quality Control

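### Section 11(3) names only the chi-square test for the Day 14 NIHSS responder comparison, although groups of 3 to 6 subjects are too small for it and the neighbouring binary comparisons allow Fisher's exact test

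*Protocol*

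**What the plan says.** Section 11(3), under the secondary efficacy endpoints, states that the proportion with an NIHSS reduction of 4 or more "points at Day 14 is compared using the chi-square test". That is the whole specification for this endpoint.

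The other binary comparisons in the protocol are worded differently:
- mRS 0-2 at Day 90, in section 11(3): it "is compared between dose groups using the chi-square test or Fisher's exact test".
- Safety, in section 11(3): "The incidence of AEs and SAEs is compared between dose groups using the chi-square test or Fisher's exact test".
- Synopsis, Statistical Analysis Methods, on differences between groups: "chi-square test or Fisher's exact test will be used for categorical variables".

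Section 11(5) sets the threshold for all tests: "Two-sided tests are used, and a P-value < 0.05 is considered statistically significant".

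Section 1(2) fixes the group sizes: "Subjects will be sequentially assigned to one of three dose groups". Each group starts with 3 subjects, and 3 more are added if one of the first 3 has a DLT. The total is 6 to 18.

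**The concern.** The Pearson chi-square p-value relies on a large-sample approximation. With nine subjects in three groups, no table comes near the expected counts that the approximation needs. The 5% level in section 11(5) is then not the level at which the test operates, and it can call a result significant when the exact test, allowed for the adjacent endpoints, does not.

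At stake is a possible false signal of a dose difference on a secondary efficacy endpoint. Because chi-square is the only test named on this line, the more favourable p-value would be the one specified by protocol, and reporting the exact result would look like a departure from section 11(3).

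**Working it through.** **Inputs.** Three dose groups of 3 subjects, or 6 if expanded (section 1(2)); two-sided 0.05 (section 11(5)); uncorrected Pearson chi-square. The NIHSS line does not say what is compared with what; I take it to be the dose groups, as in the neighbouring lines. The protocol gives no responder rate, so the common null rate *p* is an assumption and is varied. There is no power or size figure in the protocol for this comparison to reproduce beyond the nominal 5%.

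**Expected counts at 3/3/3.** With *r* responders among 9, each group expects *r*/3 responders and 3 − *r*/3 non-responders. The smaller of the two is at most 4/3 (at *r* = 4 or 5), and no expected count exceeds 3.

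**One table in full: 0/3, 1/3, 3/3.** Here *r* = 4, and the expected counts are 4/3 and 5/3 per group. The squared deviations sum to 16/9 + 1/9 + 25/9 = 42/9.
- Chi-square = (42/9) × (3/4 + 3/5) = 6.30 on 2 df, so *p* = exp(−3.15) = 0.043.
- Exact test: there are C(9,4) = 126 equally likely arrangements. The six orderings of (0,1,3) have 3 arrangements each, which makes 18, and no other table with *r* = 4 is as improbable. So *p* = 18/126 = 0.143.

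**All 64 tables at 3/3/3.** Chi-square rejects exactly the tables that contain both a 0/3 and a 3/3 group:

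| Pattern | Orderings | Chi-square p | Exact p |
|---|---|---|---|
| 0, 0, 3 | 3 | 0.011 | 0.036 |
| 0, 3, 3 | 3 | 0.011 | 0.036 |
| 0, 1, 3 | 6 | 0.043 | 0.143 |
| 0, 2, 3 | 6 | 0.043 | 0.143 |

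That is 18 rejections by chi-square and 6 by the exact test. Twelve tables are significant by chi-square only, and none by the exact test only.

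**Type I error at 3/3/3.** With *q* = 1 − *p*, the chi-square size is

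3*p*³*q*⁶ + 18*p*⁴*q*⁵ + 18*p*⁵*q*⁴ + 3*p*⁶*q*³.

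| Assumed responder rate | Chi-square size |
|---|---|
| 20% or 80% | 1.8% |
| 30% or 70% | 4.5% |
| 40% or 60% | 7.1% |
| 50% | (3 + 18 + 18 + 3)/512 = 42/512 = 8.2% |

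The size exceeds 5% for rates between about 0.31 and 0.69. The exact test peaks at 6/512 = 1.2%.

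**Other layouts the design can produce** (full enumeration, maximum over the responder rate):

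| Group sizes | Chi-square maximum | Exact maximum |
|---|---|---|
| 3/3/3 | 8.2% | 1.2% |
| 3/3/6 | 7.3% | 1.6% |
| 3/6/6 | 4.4% | 3.8% |
| 6/6/6 | 6.0% | 2.8% |
| 3 vs 3 | 3.1% | never rejects |
| 3 vs 6 | 3.9% | 2.7% |
| 6 vs 6 | 6.8% | 0.6% |

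**The case against.** **The synopsis already permits the exact test.** A responder proportion is a categorical variable, so a reader might infer from section 11(3) that the protocol as a whole rules out Fisher's test. The documents do not support that. The synopsis sentence is general, though. It follows the description of baseline variables and does not name this endpoint, while section 11(3) does name it and gives one test. What stands is a mismatch within the protocol, not a blanket prohibition.

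**The inflation depends on layout and rate.** This stands. The 8.2% needs 3/3/3 and a true rate of 50%, which is assumed. Three of the seven layouts above never exceed 5%, and at 3/3/3 neither do low or high responder rates.

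**Little depends on this test.** This also stands. A reader might take it for the only early efficacy comparison, but section 11(3) also compares mean NIHSS change, and section 5(3) includes Day 14 in that endpoint. A reader might also infer that a spurious p-value would choose the dose. Main Research Content does state an aim of determining an appropriate dose, but nothing makes this p-value a selection rule, and section 1(2) bases escalation on DLTs alone.

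**The exact test is hardly informative here.** True. Under an assumed gradient of 20%, 50% and 80% response at 3/3/3, its power is 2 × (0.512 × 0.125 × 0.512) + 2 × 0.000512 + 2 × 0.000008 = 6.7%. That is a reason to treat the comparison as descriptive. It does not justify keeping a test whose stated level does not hold.

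**Conclusion.** The point holds as a limited one. Section 11(3) fixes a test that is unsuitable for groups of 3 to 6 and differs from the wording for the neighbouring endpoints and in the synopsis. At 3/3/3, the layout when all three doses are studied without expansion, the actual level reaches at most 8.2%, an excess of about 3 percentage points, and two thirds of the tables called significant (12 of 18) fail the exact test. These table counts need no assumption about the responder rate; the 8.2% does. The consequence is a possible false secondary efficacy signal in an exploratory study. No DLT, MTD or stopping decision is touched.

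**What to change.** In section 11(3), replace the chi-square test for the NIHSS responder proportion with Fisher's exact test (Fisher-Freeman-Halton for three groups), and state that the comparison is between dose groups. This brings the line into agreement with the synopsis.

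Preferably name the exact test as the single test for the mRS 0-2 and AE/SAE comparisons too. The present wording leaves open a choice between two tests that disagree at these sizes.

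Add that the comparison is descriptive, with responders out of subjects treated shown for each dose.

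The cost is a line or two of wording, with no effect on enrolment, visits or data collection. The downside is conservatism: the exact test has size at most 1.2% at 3/3/3 and cannot reach significance at 3 vs 3, so a non-significant result must not be read as evidence that the doses are alike.
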